5.2.2. Estimand

The population of interest is adolescent, adult, and elderly non-hospitalized subjects with a confirmed influenza A infection who are at risk of developing complications.

The primary variable of interest is the time to resolution (in hours) of the 7 primary influenza-related symptoms (cough, sore throat, headache, nasal congestion, feeling feverish, body aches and pains, fatigue). Resolution is achieved if all 7 symptoms are scored as none or mild, or, are equal to or lower than the pre-influenza severity for 24 hours expressed in 3 successive recordings or 4 successive recordings where 1 in between missing recording is allowed.

The intercurrent event of use of SOC is handled in a treatment policy strategy as the primary endpoint is derived in the same way irrespective of the components of SOC, that could include influenza antivirals. For missing recordings, the composite strategy is applied. Missing recordings due to death or hospitalization are covered by using the maximum time over all subjects as the censored resolution time. Additionally, 1 missing datapoint, not due to death or hospitalization is allowed in the definition of resolution. When multiple missing recordings, not due to death or hospitalization, prevent the subject from resolving with 3 successive recordings over the full 28-day study period, censoring will be applied, but the timepoint of censoring will depend on whether the last available recording indicates resolution or not. If the last recording indicates resolution, then censoring is at the first record of resolution from the last series of recordings of resolution of influenza symptoms. If the last recording does not indicate resolution, then censoring is done at the first scheduled timepoint after the last observation.

The size of the treatment effect will be estimated by the Kaplan-Meier estimate of median time to resolution of the 7 primary influenza-related symptoms in each treatment group. A Gehan-Wilcoxon test controlling for the stratification factors will be conducted to formally compare the time to resolution of the 7 primary influenza-related symptoms between pimodivir and placebo.

5.2.3. Analysis Methods

The time to resolution of the 7 primary influenza-related symptoms will be estimated from a Kaplan-Meier analysis. The difference in time to resolution of the 7 primary influenza-related symptoms between treatment groups will be tested using a Gehan-Wilcoxon test controlling for the stratification factors, ie, type of baseline SOC and time since onset of symptoms.

Kaplan-Meier curves, overall and by stratum, and a stratified log-rank test will also be provided. Additionally, the data will be analyzed using an accelerated failure time model and a Cox

proportional hazards model. Both models will be adjusted for stratification factors and baseline symptom domain score.

These models are described in Section 5.3.2.

If the baseline symptom domain score is missing, then the baseline score will be imputed as the median score from all subjects in the ITT-i set.

Sensitivity analyses to account for missing assessments in the derivation of the primary endpoint will be performed to assess the robustness of the results of the primary analysis.

Three different imputation methods based on imputation of the resolution of the 7 primary influenza-related symptoms due to missing questionnaires on single timepoints will be implemented:

1. Impute all timepoints with missing questionnaires as resolution of the 7 primary influenza-related symptoms, but only after the first timepoint indicating resolution after the last timepoint indicating non-resolution (no later timepoints indicate non-resolution) – and subsequently derive the primary endpoint for the patient.
2. Impute all timepoints with missing questionnaires as non-resolution of the 7 primary influenza-related symptoms – and subsequently derive the primary endpoint for the patient.
3. Impute all timepoints in a consecutive series of the timepoints with a missing questionnaire as resolution of the 7 primary influenza-related symptoms, but only if this series of consecutive missing timepoints are in between 2 timepoints that indicate resolution – and subsequently derive the primary endpoint for the patient.

The statistical analysis for the primary endpoint derived after applying each of the three different imputation methods will be performed.

If no Flu-iiQ™ questionnaire is completed on a calendar day this will result in having 2 missing timepoints. To assess the amount of missing data for the primary endpoint the following tables will be provided by treatment group and overall:

1. The number and percentage of subjects completing the Flu-iiQ™ questionnaires for each analysis visit up to Day 28 visit. Subjects are expected to complete the Flu-iiQ™ questionnaire twice daily. If the subject only completes the questionnaire once for a particular analysis visit, then they will be considered as completing 50% of the questionnaires for that visit. Note that the baseline visit may occur on the same day as first administration of study drug. Subsequently, if the first dose of study drug was prior to 5pm then 2 questionnaires would be expected to be completed, and if the first dose of study drug was at or after 5pm then only 1 questionnaire would be expected to be completed on analysis visit Day 1. If the baseline questionnaire was completed the day before first dose, then one baseline questionnaire and either 1 or 2 questionnaires on the

day of first dose would be expected to be completed depending on the timing of the first dose of study drug.

2. For each subject the percentage of missing Flu-iiQ™ questionnaires will be calculated as $(1 - (\text{the number of completed questionnaires until the Day 28 visit inclusive/planned number of questionnaires})) * 100$. The planned number of questionnaires for a particular subject is 2 times the study day of the Day 28 visit – 1, plus the number of questionnaires completed at baseline. Descriptive statistics of the percentage of missing data will be produced.

The above tables will also be produced for each subgroup.

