#### 11.4. Efficacy Analyses

Descriptive statistics will be used for all efficacy endpoints and will be tabulated by treatment arm and stratification factors (baseline SOC and time since onset of symptoms).

Subgroup analyses will be performed by, but might not be limited to, region and age group.

As a confirmatory strategy, to account for multiplicity in the statistical evaluation of the most important efficacy endpoints, hierarchical testing will be applied to control for overall Type I error. The following endpoints are included in the confirmatory strategy:

1. Time to resolution of the 7 primary influenza-related symptoms (cough, sore throat, headache, nasal congestion, feeling feverish, body aches and pains, fatigue), ie, primary endpoint
2. Incidence of complications associated with influenza after the start of study treatment
3. Hospital admission rates 28 days after treatment initiation

First, the primary endpoint will be tested for superiority of pimodivir in combination with SOC over placebo in combination with SOC at the 2-sided 5% significance level. If superiority is shown on the primary endpoint, the first secondary endpoint in the sequence as indicated above

will be tested for superiority at the same significance level. If superiority is shown for this secondary endpoint, the second (and last) secondary endpoint in sequence will be tested. In case superiority is not shown for an endpoint, no further endpoints in the sequence will be tested for superiority.

For the primary endpoint, the results from the Gehan-Wilcoxon test will be used in the hypothesis testing. For the secondary endpoints, incidence of complications associated with influenza after the start of study treatment and hospital admission rates 28 days after treatment initiation, the results of the logistic regression will be used.

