### ***Primary Endpoint***

Time to resolution of the 7 primary influenza-related symptoms is defined as the time from initiation of study treatment to when all symptoms are considered resolved for at least 24 hours. A symptom is considered resolved, depending on pre-existence of the symptom:

- The symptom is pre-existing:
  - The symptom is considered resolved if post-baseline severity is equal or lower than the pre-existing severity
- The symptom is not pre-existing:
  - The symptom is considered resolved if its severity is scored at most mild post-baseline

The primary efficacy analysis of the time to resolution of the 7 primary influenza-related symptoms (cough, sore throat, headache, nasal congestion, feeling feverish, body aches and pains, fatigue) will consist of a stratified Gehan-Wilcoxon test (using the randomization stratification factors, ie, type of baseline SOC and time since onset of symptoms as strata). Kaplan-Meier curves, overall and by stratum, and a stratified log-rank test for time to symptom resolution will also be provided. Additionally, the data will be analyzed using an accelerated failure time model. Also, a Cox proportional hazards model will be applied. Both models will be adjusted for stratification factors and baseline symptom domain score.

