2.6. Other Definitions

For FDA marketing authorization approval in the US all subjects will be included in the analysis.

The oseltamivir subset (OST subset) contains only those subjects whose SOC treatment contains oseltamivir (OST). The first dose of OST may be given before the subject was randomized but should be started no later than Day 2 morning (up to noon). The complete analysis will be repeated restricted to the OST subset to support marketing authorization approval in EMA.

Analyses to support authorization approval in other regions or countries will include all subjects unless the Health Authority of the region or country requests otherwise and may be specified in a separate analysis plan and may also be reported separately.

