5.1. Analysis Specifications

5.1.1. Level of Significance

As a confirmatory strategy, to account for multiplicity in the statistical evaluation of the most important efficacy endpoints, hierarchical testing will be applied to control for overall Type I error. The following endpoints are included in the confirmatory strategy:

Primary Endpoint

- Time to resolution of the 7 primary influenza-related symptoms (cough, sore throat, headache, nasal congestion, feeling feverish, body aches and pains, fatigue)

Secondary Endpoints

- Incidence of complications associated with influenza after the start of study treatment
- Hospital admission rates 28 days after treatment initiation

First, the primary endpoint will be tested for superiority of pimodivir in combination with SOC over placebo in combination with SOC at the 2-sided 5% significance level. If superiority is shown on the primary endpoint, the first secondary endpoint in the sequence as indicated above will be tested for superiority at the same significance level. If superiority is shown for this secondary endpoint, the second (and last) secondary endpoint in sequence will be tested. In case superiority is not shown for an endpoint, no further endpoints in the sequence will be tested for superiority.

This testing procedure will be applied on the ITT-i set.

The final analysis on the ITT-i set (to support FDA marketing authorization approval) and the final analysis on the OST subset (to support marketing authorization approval in EMA) will be performed independently, using a 5% two-sided significance level for each.

Statistical Methodology for Evaluation at the Final Analysis

The p-values for the final analysis of the primary endpoint and the two most important secondary endpoints will be based on an inverse-normal combination test. For the primary endpoint, the p-values are obtained from the Gehan-Wilcoxon test. For incidence of complications associated with influenza after the start of study treatment and Hospital admission rates 28 days after treatment initiation the p-values will be obtained from a logistic regression model (see Sections 5.3.2 and 5.3.2.2).

All p-values below are one-sided p-values, to evaluate rejection of the null hypothesis that pimodivir is not better than placebo.

Let:

- p = p-value from the analysis of the ‘pre interim’ category of the ‘study period’ subgroup
- q = p-value from the analysis of the ‘post interim’ category of the ‘study period’ subgroup

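### The confirmatory Gehan-Wilcoxon test is valid but omits the baseline symptom score that the supportive models use, so a modest, conditional gain in power is forgone

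*SAP*

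**What the plan says.** Protocol 11.4 states that the primary analysis "will consist of a stratified Gehan-Wilcoxon test", with the two randomization factors as strata, and adds: "For the primary endpoint, the results from the Gehan-Wilcoxon test will be used in the hypothesis testing". SAP 5.2.2 repeats this, and SAP 5.2.3 says that the difference between arms "will be tested using a Gehan-Wilcoxon test controlling for the stratification factors, ie, type of baseline SOC and time since onset of symptoms". Under SAP 5.1.1 the final p-value "will be based on an inverse-normal combination test": the Gehan-Wilcoxon test is run separately on subjects randomized up to and after the interim cut, and the two one-sided p-values are combined. The effect size is described by Kaplan-Meier medians per arm (SAP 5.2.2).

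For the supportive AFT and Cox models, SAP 5.2.3 says: "Both models will be adjusted for stratification factors and baseline symptom domain score". A missing score takes the ITT-i median. Protocol 9.1.2 requires Module 1 on the ePRO device before randomization, because it decides inclusion criterion 2.

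For the European submission, SAP 2.6 says: "The complete analysis will be repeated restricted to the OST subset". SAP 5.1.1 gives that analysis its own two-sided 5% level.

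Neither document says why the score enters the supportive models but not the test.

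**The concern.** Resolution requires all 7 symptoms to be at most mild, or back to the pre-existing level, on 3 successive recordings (SAP 5.2.1). Entry requires only one respiratory and one systemic symptom of sufficient severity, so starting burden can run from two moderate symptoms to seven severe ones. It is reasonable to expect that burden to predict time to resolution. The SAP makes similar choices elsewhere: it adjusts the individual-symptom models for the baseline symptom score (5.3.2.1) and the viral-negativity models for baseline viral load or titer (5.3.2.4).

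The one analysis that decides superiority, opens the testing hierarchy and supplies the stage-wise p-values leaves this predictor in the noise. At stake is some power. That matters most in the less favourable rows of the plan's power table and in the oseltamivir (OST) subset, for which no size or power is stated.

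**Working it through.** **1. The plan's own power.** Inputs (Protocol 11.3): log-logistic times, scale s = 0.55, 25% reduction so |ln 0.75| = 0.2877, N = 600 randomized 1:1, two-sided 5%. For a log-logistic shift, Wilcoxon power without censoring is

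Φ( |ln 0.75| / (s·√(12/N)) − 1.96 ) = Φ( 0.2877 / (0.55 × 0.1414) − 1.96 ) = Φ(1.74) = 95.9%.

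Simulation (10,000 trials) gives 96.0% without censoring and 95.3% with 28-day censoring. The stated 90% does not reproduce. The Gehan-Wilcoxon column of Protocol Table 3 does: 97.3 / 93.0 / 94.0 / 88.6% simulated against 97.3 / 93.3 / 93.7 / 88.3% printed. Scale 0.55 lies between the table's log-logistic scales, 0.5213 (97.3%) and 0.5867 (93.3%), so 90% does not fit the table either. Table 3 is the better base for judging a gain.

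**2. What adjustment can do.** If the score explains a share R² of the variance of log time, ideal adjustment replaces s by s·√(1 − R²), which is worth about R² × N subjects: 30, 60 or 120 of 600 at R² 0.05, 0.10 or 0.20. The documents give no R², so these values are assumptions.

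**3. Simulation of the SAP's two-stage test.** Assumptions: 450 of 600 subjects before the interim, four strata, 28-day censoring, inverse-normal combination, adjustment of the Gehan scores estimated within strata, 3,000 runs per setting. The Monte Carlo SE is about 0.5 to 0.6 points at N = 600.

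| Setting | Test | R² 0 | R² 0.05 | R² 0.10 | R² 0.20 |
|---|---|---|---|---|---|
| Log-normal, scale 1.0945, N = 600 | present | 86.9 | 85.9 | 85.8 | 85.7 |
| | rank ANCOVA | 86.1 | 87.2 | 88.3 | 91.5 |
| | difference | −0.8 | +1.3 | +2.5 | +5.8 |
| Log-logistic, scale 0.5867, N = 600 | present | 91.5 | 91.0 | 91.5 | 90.7 |
| | rank ANCOVA | 91.5 | 91.9 | 93.5 | 95.9 |
| | difference | 0.0 | +0.9 | +2.0 | +5.2 |
| OST subset, assumed N = 300, log-normal 1.0945 | present | 55.1 | 56.8 | 54.5 | 56.5 |
| | rank ANCOVA | 54.2 | 56.9 | 56.7 | 63.2 |
| | difference | −0.9 | +0.1 | +2.2 | +6.7 |

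One-sided type I error (6,000 runs, R² 0 and 0.20) was 2.3 to 2.9% for every version, against a nominal 2.5%. A second simulation of the same design, also with 450 + 150 subjects, gave smaller gains: about 0.5 points at R² 0.05, 1 to 2 at 0.10 and 3 to 4 at 0.20, and a cost of about 1 point at R² 0. The ranges in the verdict span both.

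**4. Why not score strata.** Two-stage simulation with tertiles of the score as extra strata (assumed 459 + 153 subjects, 2,000 runs) changed power as follows:

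| Setting | R² 0 | R² 0.09 | R² 0.25 |
|---|---|---|---|
| Log-logistic 0.55 | −1.4 | +0.1 | +3.7 |
| Log-normal 1.0945 | −2.2 | +0.2 | +5.2 |
| Assumed OST subset of 300, log-normal | −3.2 | −0.3 | +6.6 |

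Four strata by three score groups leave 153 / 12 ≈ 13 subjects per cell after the interim, so weak prognostic strength brings a loss or nothing.

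**The case against.** The strongest reply is that nothing is wrong. The test matches the randomization, Protocol 3.2 justifies its strata as prognostic, and severity-adjusted AFT and Cox results will be reported anyway. All of that stands.

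The score may also predict less than it seems. Inclusion criterion 2 narrows the severity range, and a pre-existing symptom counts as resolved at its usual level, so a chronic severe cough raises the score without delaying resolution. This also stands, and it is why the gain can only be given as a range over R².

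The change is not just SAP wording. The test and its strata are in Protocol 11.4. The amendment histories show that power was recast on a rank basis after Health Authority feedback and that the SAP was revised for FDA comments. SAP 2.3 puts the interim cut at 28 February 2020, while SAP Amendment 3 is dated 1 July 2020. Redefining the first-stage p-value after that cut invites questions, even though only the IDMC and its support group are unblinded. This is a real cost, but it does not defeat the proposal.

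A reader might infer three stronger things that the documents do not support:
- **That the primary test is biased or its error rate is off.** It is not; type I error is the same with and without the score.
- **That 6 to 7 points of power are being lost.** That needs a correlation of 0.5 (R² 0.25), which no document supports. The larger headline, from 90% to Φ((1.96 + 1.28)/√0.75 − 1.96) = 96.3%, also starts from a power that the inputs do not give. From 96% the same formula reaches 99.0%, a gain of 3 points.
- **That the score exists for every subject.** It is required of every subject, but the schedule limits PROs to sites with approved translations, and the SAP provides for missing baseline scores.

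**Conclusion.** The point holds as a missed efficiency gain, not an error. With 600 subjects, rank ANCOVA on the baseline score would add about 0.5 to 1.5 points of power at R² 0.05, 1 to 2.5 at R² 0.10 and 3 to 6 at R² 0.20, at unchanged type I error. If the score is not prognostic, it costs at most about 1 point.

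The result rests on the assumed R², an interim at about three quarters of the subjects, and the Table 3 distributions or the planning scale of 0.55. The OST figures also rest on an assumed 300 subjects and are indicative only.

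**What to change.** - **Test.** In SAP 5.1.1, 5.2.2 and 5.2.3 and Protocol 11.4, define the stage-wise primary test as a Gehan-Wilcoxon test with the Gehan scores linearly adjusted for the baseline symptom domain score within the existing four strata (rank ANCOVA). Do not add score strata. The Kaplan-Meier medians can remain the effect measure.
- **Score.** Name it as the 7-item composite, matching the endpoint. At present Protocol Table 1 gives the symptom domain 10 items, SAP 4.1 tabulates a 10-symptom composite, and SAP 2.1.4 uses 7. Keep the median imputation. Align SAP 5.3.2, whose general AFT and Cox text omits the score, with 5.2.3.
- **Supportive analysis.** Report the present stratified test alongside.
- **OST subset.** Use the same method. SAP section 5 drops SOC type as a factor there, so adjust within the two onset strata.
- **If the present test stays primary.** Pre-specify the score-adjusted Gehan-Wilcoxon test as a sensitivity analysis.

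Cost: a small change to the test code, with no new data, plus a protocol amendment and agency notification. Because the interim cohort is already fixed, the change must be made, and the sponsor's blinding documented, before unblinding. The statistical price is at most about 1 point of power if the score proves uninformative.

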#### **9.2.1.2. Administration of Patient-reported Outcomes**

The PRO assessments will be completed by all subjects at sites where appropriate PROs and translations are available and approved. Subjects should complete the PRO assessments in a language in which the subject is fluent and literate. Study personnel will instruct subjects how to self-complete the PRO assessment. Assessment of inclusion criterion n°2 (flu symptoms severity) must be performed through the evaluation of the subject's answers to Pre-existing Symptom Questionnaire and Flu-iiQ™ Module 1 questions programmed on the ePRO device (before randomization). Subjects who develop a decreased level of consciousness or are intubated will not complete PROs.

Subjects will complete the PRO assessments electronically on a touch screen computer (ePRO device) provided for this study. The subject should be in a quiet place to complete the PRO assessments. When deciding which answer to report, subjects should not be influenced by anyone accompanying them (such as family members and friends) or study personnel; the responses should reflect the subject's interpretation and response.

Subjects' responses to the PRO questionnaires will not be reported as AEs or SAEs.

PRO completion compliance should be assessed daily by the site staff via the ePRO web platform. Reasons for missing assessment should be documented on the web platform by the site after discussion with the subject.

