5.2. Primary Efficacy Endpoint(s)

5.2.1. Definition

The primary efficacy analysis will be based on the ITT-i analysis set and consists of the analysis of the time to resolution of the 7 primary influenza-related symptoms.

Time to resolution of the 7 primary influenza-related symptoms (cough, sore throat, headache, nasal congestion, feeling feverish, body aches and pains, fatigue) is defined as the time in hours from initiation of study treatment to when all symptoms are considered resolved for at least 24 hours. A symptom is considered resolved, depending on pre-existence of the symptom:

- The symptom is pre-existing:
 - The symptom is considered resolved if post-baseline severity is equal or lower than the pre-existing severity
- The symptom is not pre-existing:
 - The symptom is considered resolved if its severity is scored at most mild post-baseline

A symptom is considered not pre-existing if the response to the question in the pre-existing symptoms questionnaire is 'None'. Any other non-missing response indicates that the symptom is pre-existing.

The time of resolution is the first of a successive series of 3 recordings in which all symptoms for each of the 3 assessments are considered resolved (as defined above) for all 7 primary influenza symptoms. The 3 successive recordings may have been done over 4 scheduled successive analysis timepoints, in case of 1 missing in between timepoint.

In case influenza symptoms are not resolved, data will be censored.

Censoring will be done as follows:

- 1) Last non-missing record(s) indicate resolution of influenza symptoms (but insufficient recordings to meet the time to resolution)

Censoring will be done at the first record of resolution from the last series of recordings of resolution of influenza symptoms

- 2) Last non-missing record does not indicate resolution of influenza symptoms

Censoring will be done after the last observation, which is 08:00 on the same day if the last observation was a diary entry from 00:01 until 02:00, 20:00 on the same day if the last observation was a diary entry from 02:01 until 14:00, and 08:00 the next day if the last entry was a diary entry from 14:01 until 00:00.

- 3) Additionally, in the following cases the subject will be censored using a time-to equal to the maximum time across all subjects:

- death,

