- if a subject had not resolved the influenza symptoms at time of hospitalization and/or during hospitalization, and no further data on symptom resolution is available

Subjects not completing the pre-existing symptom questionnaire, or completing it after study day 1, will have values for each individual question imputed with the median response category of all subjects in the ITT-i set.

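### SAP 5.2.3, imputation method 1 turns some subjects admitted with unconfirmed resolution into early recoveries, although the estimand puts them at the maximum time; method 3 can date recovery before a hospital stay

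*SAP*

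**What the plan says.** **Event.** SAP 5.2.1: "The time of resolution is the first of a successive series of 3 recordings" in which all 7 symptoms meet the resolved criterion, with one missing timepoint allowed in between. A symptom meets it if it is at most mild or, when pre-existing, no worse than before influenza.

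**Censoring.** The rules in 5.2.1 open with "In case influenza symptoms are not resolved, data will be censored". Rule 3 then sets the time to the maximum across all subjects in two cases. One is death, listed without any condition. The other is hospitalization: "if a subject had not resolved the influenza symptoms at time of hospitalization and/or during hospitalization, and no further data on symptom resolution is available".

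**Estimand.** SAP 5.2.2 separates missing diaries by cause: "Missing recordings due to death or hospitalization are covered by using the maximum time over all subjects as the censored resolution time". It tolerates a single gap only where the cause is neither death nor hospitalization.

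**Sensitivity analyses.** SAP 5.2.3 has three imputation methods.
- Method 1: "Impute all timepoints with missing questionnaires as resolution of the 7 primary influenza-related symptoms, but only after the first timepoint indicating resolution", provided no later entry shows non-resolution.
- Method 2 sets every missing timepoint to non-resolution.
- Method 3 sets a missing run to resolution, "but only if this series of consecutive missing timepoints are in between 2 timepoints that indicate resolution".

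Each ends with the same step: "and subsequently derive the primary endpoint for the patient". None mentions hospitalization or death.

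**The concern.** The estimand treats diary silence caused by admission or death as a bad outcome. Methods 1 and 3 do not ask why a diary is missing, and the endpoint is derived only after the gaps are filled. Some of the sickest subjects can therefore move from the worst outcome, or a late one, to an early success.

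Such gaps are foreseeable. Protocol 9.2.1.2 says: "Subjects who develop a decreased level of consciousness or are intubated will not complete PROs". A subject can also be admitted while all 7 symptoms meet the criterion, because return to pre-existing severity counts as resolved and because listed complications such as myocardial infarction or stroke need not raise these 7 scores.

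The analyses are there to show whether the primary result is robust to missing assessments. If they also change the handling of hospitalization, a difference from the primary result cannot be attributed to ordinary missed diaries.

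**Working it through.** The plan gives no figure for this rule, so the check has two parts: running test subjects through the written rules, then sizing the effect under stated assumptions.

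**1. Test subjects.** Diaries every 12 hours, 56 timepoints, timepoint *k* at 12 × *k* hours. Each subject starts with six unresolved entries.

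| Subject | Primary | Method 1 | Method 2 | Method 3 |
|---|---|---|---|---|
| A: one resolved entry, then admitted, no further diary | no event (maximum time) | event at 84 h | no event | no event (maximum time) |
| B: a seventh unresolved entry, then admitted, no further diary | no event | no event | no event | no event |
| C: one resolved, 10 missing in hospital, one resolved, then nothing | no event | 84 h | no event | 84 h |
| D: as C, but resolved through Day 28 | 216 h | 84 h | 216 h | 84 h |
| E: as C, but four unresolved entries after the stay, then resolved | 264 h | 264 h | 264 h | 264 h |

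The times follow from counting: 7 × 12 = 84; (6 + 1 + 10 + 1) × 12 = 216; (6 + 1 + 10 + 4 + 1) × 12 = 264.

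In A, one entry is not the three recordings that define resolution, so rule 3 applies in the primary derivation. Method 1 supplies the missing recordings; the subject then counts as resolved and, read literally, the censoring rules are never reached. Method 3 leaves A alone because no resolved entry closes the gap. In C and D later diaries exist, so rule 3 does not apply even in the primary derivation. The conflict there is only with the limit in 5.2.2 on gaps due to hospitalization.

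**2. Checking the design model.** For log-logistic times, SE = scale × √(12/N), with effect |ln 0.75| = 0.2877 and N = 600. At scale 0.5213, SE = 0.0737 and power = Φ(0.2877/0.0737 − 1.96) = 97.4%, against 97.3% in SAP Table 2. At 0.5867 it is 93.4%, against 93.3%. At 0.55 it is 95.9%, against the 90% stated in SAP 1.4. That mismatch is a separate matter: the comparison below scores the same simulated subjects both ways.

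**3. Size under method 1.** Inputs from SAP 1.4: intercept 5.0, scale 0.55, 25% reduction, 300 per arm; times censored at 672 h (28 days). Assumed inputs:
- the rate of admission before confirmed resolution with no further diary, in each arm;
- the share of those subjects whose last entry was resolved;
- an event time under method 1 uniform between 12 h and the smaller of the subject's own time and 240 h.

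Expected number switched = 300 × (placebo rate + pimodivir rate) × share; for example 300 × (0.10 + 0.05) × 0.5 = 22.5. Gehan-Wilcoxon Z, 2,000 runs per row:

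| Rate, placebo / pimodivir | Share | Switched of 600 | Mean Z, primary | Mean Z, method 1 | Change |
|---|---|---|---|---|---|
| 2% / 2% | 10% | 1.2 | 3.525 | 3.534 | +0.01 |
| 2% / 2% | 50% | 6.1 | 3.548 | 3.590 | +0.04 |
| 5% / 5% | 10% | 3.0 | 3.366 | 3.384 | +0.02 |
| 5% / 5% | 50% | 15.0 | 3.349 | 3.453 | +0.10 |
| 5% / 2.5% | 10% | 2.2 | 3.909 | 3.850 | -0.06 |
| 5% / 2.5% | 50% | 11.1 | 3.890 | 3.593 | -0.30 |
| 10% / 5% | 10% | 4.4 | 4.110 | 3.994 | -0.12 |
| 10% / 5% | 50% | 22.5 | 4.208 | 3.611 | -0.60 |

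In the last row the proportion of runs with Z above 1.96 falls from 99.2% to 95.7%.

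**4. Direction.** A second simulation put all affected subjects in one arm, with event times uniform on 24 to 144 h; the Gehan win-minus-loss score without affected subjects is 0.171. With 2% affected on placebo only, the score goes from 0.187 to 0.162, a change of -0.025/0.171 = -15%. With 2% affected on pimodivir only, it goes from 0.153 to 0.181, or +0.028/0.171 = +16%. These are extreme cases. At a share of 10% to 50%, 2% affected implies that 20% to 4% of that arm is admitted with no further diary (0.02/0.10 to 0.02/0.50).

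**The case against.** - **Rule 3 may survive imputation.** Deriving the endpoint afterwards means applying all of 5.2.1. Rule 3 asks whether the subject had resolved by or during hospitalization and whether further data exist; one entry is not resolution, and an imputed value is not naturally data. This reading is open. But the censoring list is introduced as applying to unresolved subjects, and after method 1 the subject has three resolved recordings. A programmer following the text in order would produce an event.
- **Death.** A reader might infer that a subject who dies after one resolved entry is scored as recovered. The documents do not establish that: the death item carries no condition and can be read as an override. The text is unsettled, not wrong.
- **Method 3.** A reader might infer that it too rescues a subject who dies or falls silent after one good entry. It cannot, because it needs a resolved entry on both sides of the gap.
- **Sensitivity analyses are meant to vary the handling, and method 2 goes the other way.** True, and this limits the consequence. It does not repair methods 1 and 3: the contrast between methods 1 and 2 mixes ordinary missed diaries with hospitalization gaps.
- **Harm would still be visible.** Complications and admissions are in the testing hierarchy, and mortality is analyzed directly. A claim that these analyses would conceal harm would go too far.
- **Few subjects qualify.** Protocol 3.1 asks for every effort to continue assessments in hospital. An affected subject must be admitted, have one or two fully resolved entries last, and record nothing more. This stands.

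**Conclusion.** The point holds for method 1 and hospitalization. Followed literally, 5.2.3 gives an early event where 5.2.2 and rule 3 give censoring at the maximum time. For death, the precedence of rule 3 is unstated. Method 3 has only the narrower fault of bridging a hospital stay between two resolved entries; subjects who die or have no later data are untouched by it.

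The primary test, the Kaplan-Meier medians and the testing hierarchy are unaffected. The size is probably small, but it cannot be fixed from the documents, because they give neither an admission rate nor the share of admitted subjects with a resolved last entry. The bias has no set direction: more affected admissions on placebo make method 1 understate the benefit, and more on pimodivir make it overstate the benefit. With equal rates the change is slight.

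It is still worth correcting. According to the SAP amendment history these analyses were added at the Agency's request, and as written they vary two things at once.

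**What to change.** Add to SAP 5.2.3:
- Methods 1 and 3 do not impute resolution at timepoints missing because of hospitalization or death. Those timepoints stay missing, and diaries completed in hospital are used as observed.
- Rule 3 of 5.2.1, judged on observed diaries only, takes precedence after imputation, for death as well as for hospitalization.
- Hospitalization means the same here as in rule 3. Section 5.2.1 does not define it, so state the definition once.

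Leaving the gaps missing is better than setting them to non-resolution. The admission endpoint in 5.3.1.3 counts emergency room encounters; if that definition were used, a recovered subject could be penalized for a diary missed around a brief visit.

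With this change subject A returns to the maximum time under method 1, and subject D returns to 216 h under both methods. Subject C becomes an event at 216 h under method 1, since ordinary gaps after discharge are still filled, and has no event under method 3, as in the primary derivation. B and E do not change.

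The cost is a few sentences and one programming condition on admission, discharge and death dates, with no change to trial conduct or sample size. The downside is slightly fewer imputed resolutions in methods 1 and 3.
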